## 7.2 Study Visit 2: Loading Doses

Study visit 2 will comprise 4 weeks during which the 4 loading doses of Hemlibra (emicizumab) will be administered. During study visit 2, baseline radiology (CT and/or MRI scan) will be acquired if they were not performed within 1 month of study entry and if they are not considered suitable for study purposes. The subject and/or caregiver will also be trained for self-infusion of Hemlibra (emicizumab) and trained to look for signs of adverse events.

Subjects/caregivers will be instructed on how to recognize signs/symptoms of hypersensitivity (including anaphylaxis) and obtain emergency care in the event of such reactions occurring. The Study Investigator has the discretion to provide additional training or include additional observation (eg, after the fourth loading dose), if deemed appropriate, and each subject/caregiver will be able to ask any question he or she may have prior to being deemed capable of performing subcutaneous Hemlibra (emicizumab) injections. If, despite additional training, the investigator

---

\* Vaccinations will not be charged to the study

determines that the subject/caregiver is unable to inject Hemlibra (emicizumab), a trained and proficient caregiver or local healthcare provider should be identified to administer the injections.

Subjects will be observed for a minimum of 30 minutes after the first three loading doses of Hemlibra (emicizumab).

Following each of the first 3 loading doses of Hemlibra (emicizumab), the site will call a subject who has a previous history of a clinically significant hypersensitivity reaction 24 hours after each dose to assess the status of the subject.

Additional precautions following each of these doses may also be considered, including having an extended observation period or IV access prior to dosing, etc. The Study Investigator may include these or other precautions, as deemed appropriate.

A subject utilizing a prophylactic FVIII regimen, a prophylactic bypassing agent regimen or ITI therapy must discontinue those regimens according to the schedule below and for the duration of the study.

- Subjects receiving FVIII prophylaxis must discontinue their FVIII prophylactic regimen immediately prior to their second loading dose of Hemlibra (emicizumab)
- Subjects receiving bypassing agent prophylaxis must discontinue their prophylactic regimen at least 24 hours prior to their first loading dose of Hemlibra (emicizumab)
- Subjects who are receiving FVIII ITI therapy must discontinue ITI immediately prior to their first loading dose of Hemlibra (emicizumab)

During study visit 2, a suitable quantity (at the discretion of the Study Investigator) of Hemlibra (emicizumab) will be dispensed (see **Section 6.7**).

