- Review of surgeries and procedures

*Second study visit (up to 10 days from screening visit)*

The study visit will comprise a 4-week period to administer the 4 loading doses of Hemlibra (emicizumab). This study visit will take place at the IHTC.

- Vital signs (blood pressure, pulse, temperature, and respiratory rate) and weight
- Baseline anti-drug antibody levels for Hemlibra (emicizumab) – banked plasma sample

---

\* Although this testing and documentation is considered standard of care, there are important reasons to include this in the study and budget. There are patients in the US who are not followed at a federally recognized hemophilia treatment center and this testing may be inconsistently available. In addition, there are patients who refuse entry into CDC studies where this testing is performed or refused vaccination to prevent Hepatitis A and/or B transmission. Knowing each patient's viral exposure status and vaccination history will be important to decrease risk of community acquired infections that may lead to development of AEs that could be avoided.

- Dispensation of a suitable quantity of Hemlibra (emicizumab) (quantity to be determined by the Study Investigator)
- Baseline radiology (CT or MRI) if not performed within one month of study entry or provided scans are deemed inadequate to accurately assess the extent of the pseudotumor
- Weeks 1-4
  - First 4 weekly loading doses to be administered at IHTC
- Week 4
  - Anti-drug antibody levels for Hemlibra (emicizumab) – banked plasma sample
  - Obtain data if applicable from an activity monitoring device if standardly utilized by the patient

*Subsequent study visits (annual and study close-out visits at the IHTC; other study visits with local physician)*

Subsequent study visits will occur once a quarter, as is the standard of care for patients with hemophilic pseudotumor. These study visits will take place at the medical facilities of the subject's local physician, except for the annual and study close-out visits, which will take place at the IHTC. The first subsequent study visit will be 3 months ( $\pm 2$  weeks) following the first loading dose of Hemlibra (emicizumab).

The specific requirements of each visit are listed below. Depending on when a subject enrolls and when the study ends, the subject might not participate in all study visits beyond month 24.

*Study visits at months 3, 9, 15, 21, 27, 33, 39 and 45 ( $\pm 2$  weeks)*

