### **1.3 Hemophilic Pseudotumor**

Hemophilic pseudotumor is a rare complication of hemophilia that occurs in 1-2% of patients with severe hemophilia [van Ommeren, Mooren et al. 2000]. It is observed more frequently in geographic areas where hemophilia is diagnosed late, treatment is inconsistently available, prophylaxis is not used due to resource constraints, and in patients who do not recognize that a bleeding event has occurred (eg, moderate or mild deficient patients who experience infrequent bleeds/injuries). Pseudotumors are more commonly observed in adults than pediatric patients [Magallon, Monteagudo et al. 1994] They may be present in patients with hemophilia either with or without an inhibitor and are more common in patients with inhibitors where hemostasis is less well controlled.

A hemophilic pseudotumor consists of an encapsulated progressive cystic swelling of muscle and/or bone caused by recurrent hemorrhage which can cause a serious complication to both life and limb. Pseudotumors have been reported in a wide variety of bones and soft tissues [Liu, White et al. 1988] where repeated and unresolved hematomas lead to encapsulation, calcification and progressive enlargement, with subsequent erosion of adjacent bone. Most commonly the pseudotumor occurs in the pelvis and long bones of lower extremity; they are also observed in muscles, particularly the iliacus, vastus lateralis and soleus. Pseudotumors are best treated early; if left untreated they can result in compression pressure necrosis of adjacent structures, further bleeding, infection, erosion and loss of function and/or life. Complicating early diagnosis is the fact that patients with pseudotumors may be asymptomatic or stable for long periods of time (sometimes decades) before developing complications [Ahlberg 1975, Magallon, Monteagudo et al. 1994, van Ommeren, Mooren et al. 2000].

Hemophilic pseudotumors are most readily diagnosed and monitored using CT or MRI.

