### 3.1.2 Second Study Visit [Hemlibra (emicizumab) Loading Doses]

The second study visit will take place at the IHTC up to 10 days after the initial screening visit. The purpose of the second study visit is to administer the 4 weekly loading doses of Hemlibra (emicizumab); acquire ADA data, vital signs (blood pressure, pulse, temperature, and respiratory rate) and weight; and complete baseline radiology.

Prior to the first loading dose, a banked plasma sample will be obtained to determine baseline anti-drug antibody levels for Hemlibra (emicizumab). Baseline radiology (CT and/or MRI) will also be obtained if not previously performed within one month of study entry or if provided scans are deemed inadequate to accurately assess the extent of the pseudotumor.

Subjects/caregivers will be instructed on how to inject Hemlibra (emicizumab) and how to recognize signs/symptoms of hypersensitivity (including anaphylaxis) and obtain emergency care in the event of such reactions occurring. The Study Investigator has the discretion to provide additional training or include additional observation (eg, after the fourth loading dose), if deemed appropriate, and each subject/caregiver will be able to ask any question he or she may have prior to being deemed capable of performing subcutaneous Hemlibra (emicizumab) injections. If, despite additional training, the investigator determines that the subject/caregiver is unable to inject Hemlibra (emicizumab), a trained and proficient caregiver or local healthcare provider should be identified to administer the prophylaxis injections.

The 4 loading doses will be administered once weekly for 4 weeks using the FDA-approved regimen (3 mg/kg once weekly by subcutaneous injection). Following the 4th loading dose a second banked plasma sample will be obtained to determine anti-drug antibody levels for Hemlibra (emicizumab). If the subject routinely uses an activity monitoring device and has consented to the use of data from that device during the study, then data from the time of informed consent will be collected.

During study visit 2 suitable quantities (to be determined by the Study Investigator) of Hemlibra (emicizumab) will be dispensed to the subject (see **Section 6.7**).

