### 4.2 Inclusion Criteria

Patients must meet the following criteria for study entry:

- Signed informed consent form from the subject, parent or guardian
- Diagnosis of congenital hemophilia A (baseline FVIII level <40%) with or without FVIII inhibitor, either high or low responding, regardless of titer
- Diagnosis of a hemophilic pseudotumor confirmed by radiologic assessment such as CT or MRI
- Any weight or BMI
- Medical documentation of prophylactic or episodic treatment (FVIII or bypassing agent) and the number of bleeding episodes for at least 16 weeks, and up to 6 months if available, prior to entry into the study
- Medical documentation of any need for PRBC transfusion or hospitalization for 6 months prior to entry into the study
- Subjects with a history of an inhibitor should provide documentation of the inhibitor history including date of initial diagnosis of inhibitor, peak titer, and agent utilized for hemostatic control
- Subjects with high titer inhibitors or those with low titer inhibitors who do not respond to FVIII must be willing to use rFVIIa as first line therapy for the treatment of breakthrough bleeding events
- Medical documentation of ITI therapy for subjects with a history of a FVIII inhibitor and ITI, including current FVIII inhibitor titer
- Willingness to discontinue any current prophylactic hemostatic regimen (FVIII or bypassing agent) and/or FVIII ITI therapy for the duration of the study
  - Subjects receiving FVIII prophylaxis must be willing to discontinue their FVIII prophylactic regimen immediately prior to their second loading dose of Hemlibra (emicizumab)
  - Subjects receiving bypassing agent prophylaxis must be willing to discontinue their prophylactic regimen at least 24 hours prior to their first loading dose of Hemlibra (emicizumab)

- Subjects receiving FVIII ITI therapy must be willing to discontinue ITI immediately prior to their first loading dose of Hemlibra (emicizumab)
- Willingness and ability to comply with scheduled visits, treatment plans, laboratory tests, and other study procedures, including the health-related questionnaires, activity tracking, and bleed diaries, using systems provided during the study

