## 6.10 Efficacy and Quality of Life Assessments

The primary outcome for this study is bleeding events specifically related to the pseudotumor over time; total bleeding events will also be recorded and analyzed.

All bleeding events will be recorded in the patient diary along with the following:

- The date and time of onset
- The anatomical location and severity
- The agent(s) used to control the bleed, the exact dose(s), the number of doses and the time(s) of administration
- The Study Investigator will determine whether the bleeding event was related to the pseudotumor based on a retrospective review of the clinical data

The efficacy of Hemlibra (emicizumab) will be determined by comparing the incidence of bleeding events and use of alternate hemostatic medication on study to the incidences prior to study enrollment and by changes over time.

The following should also be recorded and transmitted to the IHTC within 7 days of their occurrence:

- The admission of the subject to a hospital or medical facility (described in **Section 6.11.3**)
- Incidences of anemia that require transfusion or intervention
- All surgeries or deaths
- Any other AEs or SAEs noted and recorded by a physician

The efficacy of Hemlibra (emicizumab) will be determined by comparing the incidence of hospitalization and anemia that require transfusion or intervention on study to the incidences prior to study enrollment and by changes over time.

The following should be acquired during study visit 2 (if they were not performed within 1 month of study entry and if they are not considered suitable for study purposes) and at every annual study visit and the study close-out visit:

- Radiology (CT and/or MRI) to observe change in the size of the pseudotumor over time (ie, the progression, stabilization or regression of the pseudotumor)

The efficacy of Hemlibra (emicizumab) will be determined by the change in the size of the pseudotumor over time (ie, the control of progression, stabilization or regression of the pseudotumor).

The following will be used to determine changes in quality of life and activity level:

- Haem-A-QoL and EQ-5D-5L will be completed following screening and at every annual study visit and the study close-out visit

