## 7 STUDY ACTIVITIES

### 7.1 Study Visit 1: Informed Consent and Screening

- Informed consent signature and date
- Determination of eligibility
- Demographics (date of birth, race, gender, height)
- Weight
- Vital signs (blood pressure, pulse, temperature, and respiratory rate)
- Medical history review, including
  - Documentation of current or past infection of Hepatitis A, B and C
    - HAV:Ab
    - HBV:Ag and Ab (Core and Surface); if HBV:Ag positive, HBV viral load
    - HCV:Ab; if HCV:Ab positive, HCV viral load
  - Documentation of HIV infection (if Ab positive, viral load and CD4 count)
  - Review of at least 16 weeks, and up to 6 months if available, of data on prior use of hemostatic therapy and number of breakthrough bleeding events
  - Review of 6 months of data on prior need for hospitalization or for PRBC transfusion
  - Review of therapy prior to study entry with dose and interval and trough level if available on prophylaxis
  - Review of history of inhibitor including date of first positive test, highest documented titer and date
  - Review of concomitant medications and supplements
  - Date of development or identification of pseudotumor and documentation of radiologic (CT or MRI) scans
  - Review of surgeries and procedures
- Physical examination
- Lab screening (if adequate results are not available in the subject's medical records):
  - FVIII\*
  - aPTT
  - PT
  - VWF:Ag
  - FVIII inhibitor level (Bethesda assay)

---

\* If the subject has an inhibitor, then testing for FVIII level may not be medically necessary as FVIII is usually undetectable in such cases. Exceptions exist, such as for a patient who has mild hemophilia with an inhibitor that only recognizes infused FVIII and not endogenous FVIII.

- CBC w/diff
- CMP + direct bilirubin
- Serum pregnancy test for female subjects
- Lab screening for hepatitis (if adequate results are not available in the subject's medical records):
  - HAV:Ab
  - HBV:Ag and Ab (Core and Surface); If HBV:Ag positive, HBV viral load
  - HCV:Ab; If HCV:Ab positive, HCV viral load
- Lab screening for HIV (if adequate results are not available in the subject's medical files):
  - HIV:Ab; if HIV:Ab positive then HIV viral load and CD4 count
- Vaccinations: If the subject is not vaccinated, previously exposed, or immune to HAV and/or HBV then they will receive the first dose of the HAV and/or HBV vaccine. Subjects must follow up with their local provider to complete the recommended vaccination schedule\*

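### The rule for when a new baseline scan is needed is written with "or" in two places and "and if" in two others, so an old scan could serve as the baseline for pseudotumor size

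*Combined protocol and SAP*

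**What the plan says.** The current text states the rule for a new baseline scan four times, in two forms.

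- Synopsis, second study visit: baseline CT or MRI is done "if not performed within one month of study entry or provided scans are deemed inadequate to accurately assess the extent of the pseudotumor".
- Section 3.1.2: baseline radiology "will also be obtained if not previously performed within one month of study entry or if provided scans are deemed inadequate".
- Section 6.10: scans are acquired at visit 2 "if they were not performed within 1 month of study entry and if they are not considered suitable for study purposes".
- Section 7.2: baseline scans "will be acquired if they were not performed within 1 month of study entry and if they are not considered suitable for study purposes".

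The first two join the conditions with *or*, the last two with *and if*. Nothing says which statement governs.

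On the age of an existing scan, section 4.2 asks only for "Diagnosis of a hemophilic pseudotumor confirmed by radiologic assessment such as CT or MRI", and section 7.1 collects "Date of development or identification of pseudotumor and documentation of radiologic (CT or MRI) scans". Neither sets a date limit.

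On timing, section 7.2 places the scan within visit 2, which covers the four weeks of loading doses. The Day 0 list in 7.2.2.1 does not name it, and the screening and visit 2 tables in Appendix 2 have no CT/MRI row. In 3.1.2 the radiology sentence follows one that begins "Prior to the first loading dose, a banked plasma sample will be obtained to determine baseline anti-drug antibody levels". That suggests a pre-dose scan but does not state it.

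Size change is listed as a primary endpoint in the Synopsis, 6.10.1 and 9.5. However, 6.10 names pseudotumor bleeding as the primary outcome, and 2.2 places size among the secondary objectives.

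**The concern.** There is no control group, so each subject's baseline scan is the main reference for judging growth, stability or shrinkage on treatment. Documentation of earlier scans and the annual scans add information but do not replace it.

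If staff follow 6.10 or 7.2 as written, a scan of any age that is judged suitable can stand as the baseline. One subject's size change could then start near the first dose and another's months or years earlier. Change that occurred before treatment would be counted as on-drug change.

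Old scans are plausible here. Section 1.3 notes that "patients with pseudotumors may be asymptomatic or stable for long periods of time (sometimes decades) before developing complications". The same statement means that the pre-treatment change may be small in some subjects and not in others.

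**Working it through.** **Comparing the two forms.** I treat *inadequate* and *not suitable* as the same condition and read *and if* literally.

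| Existing scan | New scan under *or* (Synopsis, 3.1.2) | New scan under *and if* (6.10, 7.2) |
|---|---|---|
| Within one month, suitable | No | No |
| Within one month, unsuitable | Yes | No |
| Older, suitable | Yes | No |
| Older, unsuitable | Yes | Yes |

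The *or* form triggers a new scan in three cells and the *and if* form in one. They disagree in two. The recent but unsuitable scan matters less, because staff would hardly keep a scan they had rejected. The older but suitable scan is the practical risk.

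**How much of the measured interval is pre-treatment.** Inputs:

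- A = age of the scan at first dose, in months. The documents give no scan ages, so 6, 12 and 24 months are assumptions.
- For the limit of the *or* rule, I take one month (30 days) plus up to 10 days of screening (3.1.1), with study entry read as the screening visit: 40 / 30.4 = 1.32 months.
- T = months from first dose to the on-study scan. Section 7.4 counts the first quarterly visit from the first loading dose. I count the annual visits the same way, so T = 12 or 24.

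Pre-treatment share of the interval = A / (T + A).

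| A (months) | To month 12 | To month 24 |
|---|---|---|
| 1.32 | 1.32 / 13.32 = 9.9% | 1.32 / 25.32 = 5.2% |
| 6 | 6 / 18 = 33.3% | 6 / 30 = 20.0% |
| 12 | 12 / 24 = 50.0% | 12 / 36 = 33.3% |
| 24 | 24 / 36 = 66.7% | 24 / 48 = 50.0% |

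These are shares of elapsed time. They would equal shares of size change only if size changed at a constant rate, which the documents do not claim.

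**Weight of one subject.** About 10 subjects are to be treated (9.2), so each affected subject is about 1/10 = 10% of the Treated Population.

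**Timing within visit 2.** Section 7.2 does not rule out a new scan taken after the first dose. Section 9.5 drops data acquired during visit 2 from the efficacy analyses. Read literally, that would also drop a baseline scan taken then.

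**The case against.** The strongest reply is that this is a drafting slip. The literal *and if* reading would leave a recent but unusable scan in place, which nobody would intend. Sections 6.10 and 7.2 may therefore be meant as two separate triggers, in line with the Synopsis and 3.1.2. That reading is possible. But nothing in the documents imposes it, and section 7.2 is the procedural text that staff would work from.

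An investigator could also reject a stale scan as unsuitable, or order further diagnostic procedures on Day 0. That is true: the *and if* form permits an old baseline and does not force one. Suitability is not defined, however, so the outcome rests on case-by-case judgment.

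The stakes are limited in several ways:

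- The analysis is descriptive, in about 10 subjects, and no hypothesis test is specified.
- Bleeding is named as the primary outcome.
- Subject listings and per-subject analyses would show individual data.
- The annual scans measure on-drug change from month 12 onward without the baseline, although they cannot recover the first year.

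The direction of the error is also not fixed. Earlier growth would count against the drug, earlier shrinkage would count for it, and a stable lesion would change little. These points limit the impact but leave the conflict in place.

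**Conclusion.** The concern holds. The current text gives two forms of the rule and no way to choose between them. Taken literally, they disagree in two of four situations. Followed as written, 6.10 and 7.2 allow a scan of unlimited age to be the reference for a listed primary endpoint, and 7.2 leaves open a scan taken after dosing has begun.

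Confidence in the textual conflict is high. Its effect on the size result cannot be estimated, because the number of subjects affected, the scan ages and the rate of size change are all unknown. Under the assumed ages of 6 to 24 months, between one third and two thirds of the baseline-to-month-12 interval would precede treatment, against about 10% at the limit of the *or* rule. It should be fixed: the flaw is in a stated rule and can bias a listed primary endpoint.

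**What to change.** 1. Use the *or* wording of the Synopsis and 3.1.2 in sections 6.10 and 7.2.
2. State in 7.2 and 7.2.2.1 that any new baseline scan is completed before the first loading dose.
3. Optionally, add a clause to 9.5 that the visit 2 exclusion does not apply to the baseline scan.

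While the text is open, it would help to say which date counts as study entry for the one-month window and to add a baseline CT/MRI row to Appendix 2.

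The cost is wording in three sections plus the optional additions. In practice it means an occasional repeat scan, already provided for in the Synopsis and 3.1.2. It may also need some scheduling effort, since visit 2 falls up to 10 days after screening. The change concerns how an endpoint is measured and does not alter dosing or clinical care.
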